### **5.3. Exclusion criteria**

- Inability to provide patient's directives about the notification of individual study results on genetic variants of SOD1, C9orf72, FUS and TARDBP
- Inability to comply with study requirements
- Unspecified reasons that, in the opinion of the site investigator, perceiving the subject unsuitable for enrollment

### **6. Enrollment of subjects**

The enrollment of subjects takes place in specialized ALS-outpatient centers in Germany. ALS patients being eligible for the investigation, will be invited to participate in this cohort study. After obtaining informed consent, subjects will be enrolled in the study. Approximately, 2,000 subjects will be observed in this study. Participating sites will be informed once 2,000 subjects have been enrolled.

### **7. Withdrawal of subjects**

Subjects must be withdrawn from the study for any one of the following reasons:

- The subject withdraws informed consent
- The subject is unwilling or unable to comply with the protocol
- At the discretion of the investigator

The reason for the subject's withdrawal from the study must be recorded. In case of withdrawal before the end of the genetic investigation, another patient can be enrolled to surrogate the other.

### **8. Study procedures and data processing**

#### **8.1. Study procedures**

Subjects will be registered at baseline, after the investigator has verified the eligibility of the subjects by means of inclusion and exclusion criteria. After obtaining informed consent, all data defined in the protocol will be collected from different sources:

- Data capture from medical records (registry): clinical characteristics, family history, interventions and health care measures
- Assessment and data capture at study site (on-site assessment): clinical characteristics, family history, interventions and health care measures, self-assessment scales (ALS-FRS, MYMOP)
- Assessment and data capture from remote (digital self-assessment): self-assessment scales (ALS-FRS, MYMOP)
- Assessment and data capture at molecular genetic laboratory (genetic analysis): genetic variants in the genes of SOD1, C9orf72, FUS and TARDBP
- Capture from APST platform (registry): provision with assistive technology devices

## **8.2. Data collection**

Data will be collected from various sources and by different means. Some data are obtainable retrospectively as from medical records (at study sites) and platform-based registry (APST platform). Other data will be collected prospectively using on-site or assessments.

Data defined in the protocol will be assessed and captured by different means:

- Data from medical records and on-site assessments: data on clinical characteristics, family history, interventions and health care measures) will be collected on data sheets and transferred to predefined data fields on the web-based study software “studioMED+” or may be captured on the electronic case report form (eCRF) of “studioMED+” directly.
- Data from remote assessment: data from digital self-assessments (ALS-FRS, MYMOP) will be captured on a smart phone application (“ALS-App”) and stored in the data base of the APST platform (<https://www.ambulanzpartner.de/>). The “ALS-App” serves as a mobile application of the APST platform.
- Data from genetic laboratory: molecular genetic analysis will be performed on blood samples provided by study participant. Results from the genetic investigation will be generated by the genetic laboratory and transferred to predefined data fields on the web-based study software “studioMED+”.
- Data on health care measures: data on the provision with assistive technology (complex power wheelchairs, communication devices, robotic assistive systems, symptomatic pharmacotherapy, physical, occupational and speech therapy will be captured on the APST platform directly.

## **8.3. Molecular genetic analysis**

Molecular genetic analysis will be performed by a qualified and certified (ISO15189) laboratory. The procedures undertaken include DNA isolation from blood samples collected in EDTA tubes and DNA quality analysis. QF-PCR and RT-PCR analysis of the C9orf72 will be performed for repeat expansion analysis. Pathogenic repeat expansions as determined by PCR will be confirmed by Southern blot. Molecular genetic analysis of SOD1, FUS and TARDBP will be carried out by sequencing of the coding region of the SOD1, FUS and TARDBP gene. Bioinformatics, diagnostic analysis, confirmation of the positive result in an independent experiment, as well as interpretation of genetic variants will be delivered by the service provider. The molecular genetic analysis and all associated services will be provided by ARCHIMED Life Science GmbH (ARCHIMEDlife), Vienna (Austria).

## 9. Assessments

### 9.1. Demographic data

Demographic data will be collected as follows:

*Table 2: Items used to describe demographic data*

Item	Description
Date of Birth	MM/YYYY
Gender	Male Female
Place of residence	PLZ (first 3 digits), NNNXX

### 9.2. Social characteristics

Data on social characteristics will be collected as follows:

*Table 3: Items used to describe social characteristics*

Item	Description
Marital status	married single divorced widowed
Highest level of education	No formal education Primary school Secondary school Advanced or higher certificate Bachelor's degree or national diploma Postgraduate diploma/Master's degree Doctorate (PhD)
Employment status	Student Working for payment or profit Unemployed Retired from employment Looking after home/family Unable to work due to permanent sickness or disability Other (Please specify)
Working hours in employment	Working hours per week
Living arrangement	Own home Assisted living Nursing home Hospice

### 9.3. Disease history

Data on disease history will be collected as follows. Onset of ALS will be defined at time of paresis in extremities, dysarthria or dysphagia.

Table 4: Items used to describe the disease history

Item	Description
Date of onset	MM-YYYY
Date of diagnosis	MM-YYYY
Age of onset	YY
Duration of disease	MM
Data of death (if applicable)	MM-YYYY

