## 1. Visit schedule

Table 1: Visit schedule

Visit schedule	V1 M1-M3 (Baseline)	V2 M4-M8* (Follow-Up)	V3 M9-M14 (Closure)
Demographic data			
Age	x		
Gender	x		
Place of residence	x		
Social characteristics			
Employment status	x		
Marital status	x		
Education level	x		
Living arrangement	x		
Disease history			
Date of disease onset	x		
Date of initial diagnosis	x		
Age at disease onset	x		
Duration of disease	x		
Date of death (if applicable)			
Family history			
Family members who are living with ALS	x		
Family members who died of ALS	x		
Family members who are living with FTD	x		
Family members who died of FTD	x		
Family members who are suffering from neurological/psychiatric disorder	x		
Family members who died of any neurological/psychiatric disorder	x		
Clinical classification			
ALS subtypes	x		
Region of onset	x		
Functional deficits and progression			
ALS Functional Rating Scale (ALS-FRS)	x	x(2)	x
ALS progression rate (loss of ALS-FRS per month)	x	x(2)	x
King's classification of clinical stages of ALS	x		x
Serum neurofilament light chain (sNFL)	x	x(2)	X(2)
Interventions and health care measures			
Use of PEG	x		x
Use of non-invasive ventilation	x		x

Use of tracheotomy	x		x
Provision of a manual wheelchair (1)	x		
Provision of complex power wheelchair (1)	x		
Provision of a communication device (1)	x		
Provision of assistive technology (1)	x		
Physical, occupational and speech therapy (1)	x		
Riluzol and symptomatic pharmacotherapy (1)	x		
Treatment expectation			
MYMOP2, measure yourself outcome profile	x	x(2)	x(2)
Molecular genetic analysis			
C9orf72	x		
FUS	x		
SOD1	x		
TARDP	x		

M: month, V: visit; 1 = subgroup of users of APST management platform, 2 = in subgroup of patients with SOD1 mutation data will be collected more frequently (up to monthly collection of existing data of sNfL; up to weekly self-assessment of ALS-FRS using the ALS-App in addition to on-site assessment of ALSFRS-R during site visits). In the main cohort of non-SOD1 patients the collection of sNfL data is limited to the visits V1 (baseline) and V2 (follow-up).

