##### *Demographic data, disease history and social setting*

- Age, gender, place of residence
- Disease onset and duration
- Education, employment, housing

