##### *Clinical classification*

- ALS subtypes (classic ALS, progressive muscular atrophy (PMA) and primary lateral sclerosis (PLS))
- Type of onset (bulbar region, trunk or extremities)

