### **5.2. Inclusion criteria**

Being eligible to participate in this study, study candidates must meet the following eligibility criteria at the baseline assessment:

- ALS, including classical ALS, Progressive Muscle atrophy (PMA) or Primary Lateral Sclerosis (PLS)
- Ability to understand the purpose and risks of the study and provide signed and dated informed consent and authorization to use protected health information (PHI) in accordance with national and local subject privacy regulations
- Age of 18 years old at the time of informed consent

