## 9.5. Clinical classification

Data on clinical classification will be collected as follows:

*Table 6: Items used to describe clinical classification*

Item	Description
ALS subtypes (domination of upper or lower motor neuron)	Classical ALS Progressive Muscle Atrophy (PMA) Primary Lateral Sclerosis (PLS)
Type of onset (region of onset)	Bulbar region Trunk Upper extremities Lower extremities

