### 9.6.2. ALS progression rate

The ALS progression rate ( $\Delta$ ALS-FRS) can be derived from the ALS-FRS. The loss of ALS-FRS value per month, or delta ALS-FRS, indicates the rate of deterioration and predicts survival (Kimura et al. 2006).  $\Delta$ ALS-FRS is calculated using the following formula:

$$\Delta\text{ALS-FRS} = \frac{(48-\text{ALSFRSR})}{\text{Duration of disease since diagnosis (months)}}$$

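### Trunk is a codable region of onset, but the rule for dating onset in section 9.3 contains no trunk sign, so date and region of onset can describe different events

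*Combined protocol and SAP*

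**What the plan says.** Section 9.3 defines onset once: "Onset of ALS will be defined at time of paresis in extremities, dysarthria or dysphagia". The list is closed. It offers no example wording, no catch-all and no fallback for a patient who starts in another way. Table 4, in the same section, collects date of onset and date of diagnosis by month and year, age of onset in years and duration of disease in months.

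Section 9.5, Table 6, codes the region of onset as "Bulbar region Trunk Upper extremities Lower extremities". Section 3.4.2 makes the same item an additional endpoint: "Type of onset (bulbar region, trunk or extremities". The synopsis describes it by where the first symptoms appeared.

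The onset date feeds the additional endpoint "Disease onset and duration" in section 3.4.2 and the item "Age at disease onset" in Table 1, which is collected at V1 only. The progression rate in section 9.6.2 has a different time base: "Duration of disease since diagnosis (months".

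**The concern.** Region of onset and date of onset should describe the same event, namely the first manifestation of the disease. For three of the four regions in Table 6 they do. For the trunk they cannot, because the date has to wait for a sign in a different region. A site that follows section 9.3 literally would record the trunk as the region and a later limb or bulbar sign as the date. Another site might date the first trunk sign, and a third might leave the field empty. With about 18 centres the handling could vary by site.

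Where the rule is followed, the error has one direction: onset is recorded too late and age at onset too high. Both are baseline characteristics, and section 11 applies its tests to baseline characteristics of the genetically defined subsets. What is at stake is the accuracy of a descriptive additional endpoint in a small phenotype and the internal consistency of those records.

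**Working it through.** The plan states no figure that depends on this rule, so there is none to reproduce. The check sets the passages side by side and then sizes the gap on stated assumptions.

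**Step 1. Match each Table 6 region to a dating sign in section 9.3.**
- Bulbar region: dysarthria or dysphagia. Covered.
- Upper extremities: limb paresis. Covered.
- Lower extremities: limb paresis. Covered.
- Trunk: no sign listed. Not covered.

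No other section gives a second definition of onset or says how to date onset in the trunk.

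**Step 2. Trace which items use the onset date.**
- Date of onset (Table 4): affected directly.
- Age of onset (Table 4, Table 1): affected, but recorded in whole years.
- Duration of disease (Table 4): the start point is not stated. It is affected only if counted from onset.
- Progression rate (section 9.6.2): divides by months since diagnosis. Not affected as written.
- Variant frequency, the primary endpoint (section 3.4.1): not affected.

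**Step 3. Size.** The documents give neither the share *s* of trunk-onset patients nor the delay *d* to the first limb or bulbar sign. Assumed: *s* = 1% to 5%, *d* = 3 to 12 months. Planned enrolment is 2,000 (section 5.1).
- Patients affected, at most: 0.01 × 2,000 = 20 to 0.05 × 2,000 = 100. This is a ceiling, because it supposes that every trunk-onset patient is dated by the literal rule and that none had a listed sign at the same time.
- Shift in the cohort mean of time since onset: *s* × *d*, from 0.01 × 3 = 0.03 to 0.05 × 12 = 0.6 months.
- Shift within the affected patients: *d* itself, 3 to 12 months. Recorded age at onset moves by 0 or 1 year.

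**Step 4. One patient.** Suppose trunk weakness begins 18 months before V1 and limb paresis 10 months before V1 (both assumed). Onset is recorded 18 − 10 = 8 months late. If duration is counted from onset, it is short by 8/18 = 44%.

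**Step 5. Comparison between genotype groups.** Each group's mean moves by its own *s* × *d*. With the same share and delay in both groups, the shifts cancel. With shares of 1% and 5% and a delay of 8 months in both, the difference is (0.05 − 0.01) × 8 = 0.32 months. The documents do not say that the shares differ.

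**The case against.** The case for leaving the text alone is that this is a wording mismatch in an additional endpoint of a study that tests no formal hypothesis. Clinical characteristics are also drawn from medical records (sections 8.1 and 8.2), so a site may well hold the true date of the first trunk symptom. Nothing in the protocol says the field would be left blank. This limits the importance of the point but does not remove it. A date available in the records still fails the definition in section 9.3, and the protocol gives sites no instruction to prefer it.

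A reader might infer three stronger things. The documents support none of them.

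- *That PLS patients as a group are dated late.* PLS is eligible under section 5.2, and Table 6 separates subtypes by upper or lower motor neuron predominance. The documents do not say how PLS presents. A PLS patient whose first sign is on the list is dated normally. Any patient, with PLS or not, whose first motor sign is off the list would be misdated in the same way, but how often that happens cannot be read from the protocol.
- *That the planned progression rate is inflated.* Section 9.6.2 divides by months since diagnosis, so a late onset date does not enter it, and the protocol defines no onset-based rate.
- *That the genotype comparison is biased.* For that, trunk onset or the delay would have to be unevenly distributed across genotypes, and no section says so.

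**Conclusion.** The contradiction between section 9.3 and Table 6 is real: one of the four codable regions has no dating sign. It goes beyond missing detail, because the rule as stated gives a late date, or none at V1, for a trunk-onset patient without a limb or bulbar sign. Date of onset and age at onset are clearly affected. Duration of disease is affected only if Table 4 means duration from onset.

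The effect is probably small: no more than 20 to 100 patients, and 0.03 to 0.6 months on the cohort mean. Both ranges rest wholly on the assumed trunk share, and the second also on the assumed delay. Within the affected records the date could be wrong by the full delay. The point is minor: worth correcting because the correction is cheap, with no bearing on the primary objective.

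**What to change.** Reconcile section 9.3 with Table 6. Suggested wording: *Date of onset is the month of the first motor sign attributed to ALS in the region of onset recorded in Table 6 (bulbar region, trunk, upper extremities or lower extremities).* This covers the trunk. Because it refers to the first motor sign and not to a closed list, it also covers any patient whose first sign is not among the present three, without a separate rule by subtype.

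Add an eCRF check at V1 asking the site to confirm that date and region of onset refer to the same event. Query records already entered with the trunk as region of onset.

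The cost is one sentence, one edit check and a small number of queries: on the assumed share, at most 20 to 100 at full enrolment. The change concerns a data definition only and adds no assessment for patients.

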#### 9.4. Family history

The number and degree of relatedness of family members who are living with ALS (or FTD) or who died of ALS (FTD) will be investigated. Furthermore, family members suffering from any neurological/psychiatric disorder or who died of any neurological/psychiatric disorder will be determined. A first-degree relative (FDR) is a person's parent (father or mother), full sibling (brother or sister) or child. It constitutes a category of family members that largely overlaps with the term nuclear family, but without spouses. A second-degree relative (SDR) is someone who shares 25% of a person's genes. It includes uncles, aunts, nephews, nieces, grandparents, grandchildren, half-siblings, and double cousins.

Table 5: Items used to describe the family history of ALS or FTD

Item	1 st degree relative (n)	2 nd degree relative (n)
ALS (living)	Suspected Probable Definite Genetically confirmed	Suspected Probable Definite Genetically confirmed
ALS (deceased)	Suspected Probable Definite Genetically confirmed	Suspected Probable Definite Genetically confirmed
FTD (living)	Suspected Probable Definite Genetically confirmed	Suspected Probable Definite Genetically confirmed
FTD (deceased)	Suspected Probable Definite Genetically confirmed	Suspected Probable Definite Genetically confirmed
Neurological/psychiatric disorder (living)	Definite	Definite
Neurological/psychiatric disorder (deceased)	Definite	Definite

n = number of individuals

## 9.5. Clinical classification

Data on clinical classification will be collected as follows:

*Table 6: Items used to describe clinical classification*

Item	Description
ALS subtypes (domination of upper or lower motor neuron)	Classical ALS Progressive Muscle Atrophy (PMA) Primary Lateral Sclerosis (PLS)
Type of onset (region of onset)	Bulbar region Trunk Upper extremities Lower extremities

## 9.6. Functional deficits and progression

### 9.6.1. ALS Functional Rating Scale

The functional impairment will be described by using the ALS functional rating scale (ALS-FRS). The ALS-FRS is a questionnaire that is frequently used in ALS, in order to describe functional impairment (Cedarbaum et al. 1999). Furthermore, motoric function and skills of arms and legs, the bulbar function as well as the respiratory function is described. Interventions in the areas of nutrition and ventilation as well as the ability to use communication devices are also targeted. The questionnaire contains 12 short, clear questions, each with five possible answers (0-4). In total, 0 to 48 points can be achieved. The lower the number of points achieved, the higher the defined degree of severity of the functional impairment. The online assessment of ALS-FRS complements the well-established face-to-face application of the ALS-FRS (Maier et al. 2012).

### 9.6.2. ALS progression rate

The ALS progression rate ( $\Delta$ ALS-FRS) can be derived from the ALS-FRS. The loss of ALS-FRS value per month, or delta ALS-FRS, indicates the rate of deterioration and predicts survival (Kimura et al. 2006).  $\Delta$ ALS-FRS is calculated using the following formula:

$$\Delta\text{ALS-FRS} = \frac{(48-\text{ALSFRSR})}{\text{Duration of disease since diagnosis (months)}}$$

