#### **3.3. Additional objectives**

The additional objectives of this study are as follows:

- To investigate the demographic and social characteristics
- To investigate the family history for ALS or FTD
- To investigate the clinical classification, functional deficits, disease progression and health care measures in a subset of ALS patients with pathogenic variants in the genes of SOD1

or C9orf72 as compared to ALS patients with no ALS-associated mutations in the investigated genes

- To register available data on serum concentration of neurofilament light chain (sNfL)
- To register the history of interventions and health care measures including percutaneous endoscopic gastrostomy (PEG) and ventilation therapy
- To register the provision with assistive technology devices, symptomatic pharmacotherapy and physical, occupational and speech therapy
- To identify patient's treatment expectations towards ALS therapy using the Measure Your Medical Outcome Profile (MYMOP2)

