### 9.6.3. King's clinical stage of ALS

The course of disease was classified according to the King's clinical stage of ALS (Balendra et al. 2014). Stage 1: involvement of one clinical region; Stage 2: involvement of second clinical region; Stage 3: involvement of third clinical region; Stage 4: nutritional or respiratory failure.

*Table 7: Items used to describe functional deficits and progression*

Item	Description
ALS-FRS	ALS-FRS, total score ALS-FRS, score points per item (1-12)
ALS progression rate	Loss of ALS-FRS score points per month
King's clinical ALS stages	Stage 1-4

Neurofilament light chain (sNfL)	Serum concentration of neurofilament light chain (sNfL) in pg/mL
----------------------------------	--

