## **11. Statistical methods and analysis plan**

Descriptive statistics will be presented for each assessment of all subjects at study visit. Subgroup analyses by genetic or clinical criteria or other baseline characteristics will be performed. Secondary endpoints in the genetically defined subsets of ALS with confirmed SOD1 or C9orf72 mutations will be compared to genetically tested patients with ALS not revealing any ALS-associated mutation in any of the tested genes. Descriptive statistics will be used for the statistical analysis (frequency in percentage, mean, median, standard deviation in  $\pm$ , interquartile ranges (Q1, Q3), and ranges (min, max). The standardized mean difference (SMD) will be applied in this study. The SMD of each measure over up to 12 months will be estimated using the change in measure between each subject's assessments and within each individual. The standardized mean difference expresses the size of intervention effect. Difference of frequencies between two groups will be assessed by Fisher's exact test or Chi-square test, or within metric data by using the Shapiro-Wilk test, Kruskal-Wallis test and Mann-Whitney U-test. The Wilcoxon test will be employed for the analysis of statistical power of ordinal-scaled data, while metric data were subjected to the t-test (ALS-FRS, MYMOP). This analysis applies to the comparison of genetically defined subsets of ALS (baseline characteristics and changes over time). The analysis of follow-up data is limited to complete

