cases, since not all patients are expected to complete end-of-study assessments due to disease progression, e.g., death. It is aimed to compare the baseline characteristics and the proportion of death between those who completed and not those not completed 6 months and 12-month assessment. Statistical significance will be ascertained by according to an error risk of up to 5% (p-value < 0.05). Associations for the clinical outcomes will be assessed by linear regression models adjusted for potential confounding factors. Results of the longitudinal observations will be also controlled for the influence of any covariate (sex, age, intervention history). Longitudinal analysis by means of group comparisons will be applied by using a multivariate analysis. 95% confidence intervals with p-values will be reported. In order to draw conclusions from the samples with censored data, missing data records will be omitted and treated as missing values. Data analysis will be performed using SPSS (Version 25.0).

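### The ALS progression rate divides loss counted from the full score of 48 by months since diagnosis, so it measures diagnostic delay and time since diagnosis as well as decline

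*Combined protocol and SAP*

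**What the plan says.** Section 9.6.2 gives the only formula for the progression rate: (48 − ALSFRSR) divided by "Duration of disease since diagnosis (months". It describes the result in these terms: "The loss of ALS-FRS value per month, or delta ALS-FRS, indicates the rate of deterioration and predicts survival". Section 9.6.1 sets the scale at 0 to 48, with lower scores meaning more impairment, so 48 is the unimpaired state.

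Section 9.3 treats onset as an event of its own: "Onset of ALS will be defined at time of paresis in extremities, dysarthria or dysphagia". Table 4 lists the dates of onset and diagnosis as separate items, each to the month, and Table 1 collects both at V1. Table 4 also lists a duration of disease without saying where it starts.

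Elsewhere the rate is only named. Table 1 schedules it at V1, V2 and V3 as "ALS progression rate (loss of ALS-FRS per month"), and Table 7 calls it "Loss of ALS-FRS score points per month". Section 3.4.2 makes it an additional endpoint. Section 3.3 sets out to compare "disease progression and health care measures in a subset of ALS patients with pathogenic variants in the genes of SOD1" or C9orf72 with patients in whom no mutation was found. On analysis, Section 11 states: "The SMD of each measure over up to 12 months will be estimated using the change in measure between each" subject's assessments. On adjustment it states: "Results of the longitudinal observations will be also controlled for the influence of any covariate (sex, age, intervention history").

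**The concern.** The numerator and denominator cover different periods. Loss is counted from the unimpaired state, so it includes everything lost before diagnosis, while time is counted only from diagnosis. Two patients declining equally fast get different rates if one was diagnosed later after onset, or was assessed sooner after diagnosis. The inclusion criteria in Section 5.2 set no limit on time since diagnosis, so very different values can be mixed in one comparison.

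Three things are at stake:

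- **Description.** The reported figure is not points lost per month, which is what Tables 1 and 7 call it.
- **Genotype comparison.** If delay or time since diagnosis differs between carriers and non-carriers, the rate can show a difference that does not exist or conceal one that does. Neither quantity is among the covariates named in Section 11.
- **Change over time.** Read literally, the standardized mean difference applies to the change in every measure, including this rate. The rate tends to fall as time since diagnosis grows, even in a patient whose decline is constant.

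The rate is also undefined for an assessment in the month of diagnosis, and no rule covers that case. The title of the source cited for the rate refers to the rate at the time of diagnosis. Going by the title alone, that is the point at which this denominator is zero.

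**Working it through.** The plan states no numerical rate, power or sample size for this endpoint, so there is no figure to reproduce. The check is algebra on the Section 9.6.2 formula.

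**Inputs.** From the documents: reference score 48 and the denominator in months since diagnosis. Assumed, because the documents give no values: constant decline of r points per month from 48 at onset; delay d from onset to diagnosis of 6 to 12 months (18 in one example); t months from diagnosis to assessment; V3 12 months after V1.

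**Formula.** Loss at assessment is 48 − score = r(d + t). The protocol rate is therefore r(d + t)/t = r(1 + d/t). This exceeds r whenever d > 0 and has no value at t = 0.

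**Inflation and apparent fall.** Inflation is 1 + d/t. The apparent fall from V1 to V3 under constant decline is 1 − [1 + d/(t + 12)]/[1 + d/t], with t taken at V1.

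| t (months) | Inflation, d = 6 | Inflation, d = 12 | Fall, d = 6 | Fall, d = 12 |
|---|---|---|---|---|
| 3 | 3.00 | 5.00 | 53.3% | 64.0% |
| 6 | 2.00 | 3.00 | 33.3% | 44.4% |
| 12 | 1.50 | 2.00 | 16.7% | 25.0% |
| 24 | 1.25 | 1.50 | 6.7% | 11.1% |
| 60 | 1.10 | 1.20 | 1.5% | 2.8% |

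**One patient followed over time.** Take r = 0.5 and d = 12. At t = 2, 8 and 14 the scores are 41, 38 and 35, and the protocol rates are 7/2 = 3.5, 10/8 = 1.25 and 13/14 = 0.93. The true rate is 0.5 throughout.

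**A real difference hidden.** Both groups are at t = 6. With r = 1.0 and d = 6, loss is 1.0 × 12 = 12. With r = 0.667 and d = 12, loss is 0.667 × 18 = 12. Both score 36 and both rates are 12/6 = 2.0, so a 1.5-fold true difference disappears.

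**A difference created.** With equal r and delays of 12 and 6 months, the ratio of rates is (t + 12)/(t + 6): 18/12 = 1.5 at t = 6, 36/30 = 1.2 at t = 24 and 72/66 = 1.09 at t = 60.

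**Order reversed.** With r = 0.5, d = 18, t = 3 the rate is 0.5 × 21/3 = 3.5. With r = 1.0, d = 6, t = 6 it is 1.0 × 12/6 = 2.0. The slower patient appears faster.

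**If decline is not constant.** Let loss be k(d + t)^p. The rate falls from V1 to V3 when p < ln[(t + 12)/t] / ln[(d + t + 12)/(d + t)]. The limits are:

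| t at V1 (months) | d = 6 | d = 12 |
|---|---|---|
| 3 | 1.90 | 2.74 |
| 6 | 1.58 | 2.15 |
| 12 | 1.36 | 1.71 |
| 24 | 1.21 | 1.41 |

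Above these values the rate rises instead. The apparent slowing therefore holds for constant or moderately accelerating decline, and the margin shrinks as time since diagnosis grows.

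**With onset as the start.** The rate becomes r(d + t)/(d + t) = r for every d and t. A between-visit slope also returns r under constant decline.

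**The case against.** The strongest reply concerns weight, not correctness. The rate is one of many additional endpoints in an evaluation that Section 3.4.2 calls exploratory, with no formal hypothesis. No eligibility or sample size decision depends on it. Both dates are collected, so the rate can be recomputed at any time before analysis. All this stands. It means the error is cheap to repair; it does not make the formula right.

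Section 11 also provides for linear regression adjusted for potential confounders that it does not name. Delay or time since diagnosis could be among them, but neither is specified. The distortion is multiplicative and nonlinear in time since diagnosis, so adding the two as linear terms would not reliably remove it.

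The apparent-slowing argument depends on applying the standardized mean difference to a quantity that is already a rate. Section 11 names ALS-FRS and MYMOP as metric data and never names change in the rate. That argument is therefore secondary.

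The largest factors belong to patients assessed soon after diagnosis. At 60 months the inflation is only 1.10 to 1.20, so 3 to 5 times should not be read as typical. Bias between genotypes also needs a group difference in delay or time since diagnosis, which the documents do not show.

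**Conclusion.** The concern holds: the formula is wrong as written. It is the only definition in the plan, and whenever diagnosis follows onset and the score is below 48, it overstates average monthly loss since onset. That conclusion needs no assumption about the size of the delay, and constant decline is used only to put numbers on it. The size rests on assumed delays of 6 to 12 months and ranges from 3 to 5 times at 3 months after diagnosis down to 1.1 to 1.2 times at 60 months.

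Bias in the genotype comparison is possible but not established. If it arises, a 1.5-fold difference in either direction is within reach at 6 months after diagnosis. The primary endpoint and the raw ALS-FRS change are untouched.

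**What to change.** 1. In Section 9.6.2, make the denominator the months from symptom onset (date of onset, Table 4) to the assessment.
2. Define duration of disease in Table 4 in the same way. Table 6 allows onset in the trunk, which the Section 9.3 definition of onset does not mention, so state which date counts for those patients.
3. State how a zero denominator is handled, for example set to missing with the count reported.
4. Do not use change in this rate as the measure of in-study progression, because the onset-based rate is still a cumulative average. Use ALS-FRS change from V1 divided by the actual months elapsed, or a slope fitted to all available scores. Section 11 already plans to use change between assessments, so this mainly adds the division by elapsed time and makes clear which measure serves the comparison.

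The cost is small: a formula, a clarified definition, a handling rule and a sentence in Section 11. The onset date is collected at V1, so no new data are needed, and rates already calculated can be recomputed.
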